5.2 Exclusion criteria

Participants fulfilling any of the following criteria are not eligible for inclusion in this study.

Screening period up to liver transplantation

- 1. Use of other investigational drugs at screening, within 30 days or 5 half-lives of screening (until the expected pharmacodynamics effect has returned to baseline), whichever is longer.
- 2. Recipients of multiple solid organ or islet cell transplants have previously received a tissue transplant, or recipients who have a combined liver-kidney transplant.
- 3. Recipients of a liver from a donor after cardiac death (DCD), from a living donor, or of a split liver.

- 4. Not-applicable
- 5. Recipient who tests negative for Epstein Barr virus (EBV) within 28 days prior to baseline visit.
- 6. Patients who have received a live vaccine within four weeks prior to transplantation.
- 7. Recipients receiving an ABO incompatible allograft.
- 8. History of malignancy of any organ system (except hepatocellular carcinoma or localized basal cell carcinoma of the skin), treated or untreated, within the past 5 years, regardless of whether there is evidence of local recurrence or metastases.
- Hepatocellular carcinoma that does not fulfill Milan criteria (1 nodule ≤5 cm, 2-3 nodules all ≤3 cm, without evidence of metastatic disease or vascular invasion, see Appendix 2, Mazzaferro et al 1996) at the time of transplantation.
- 10. Participants transplanted for acute liver failure (does not apply to acute on chronic liver failure).
- 11. Any use of antibody induction therapy or use of any immunosuppressive or other medications prohibited by the protocol (see Section 6.2.2).
- 12. Recipients with history of non-liver related coagulopathy or medical condition requiring long-term anticoagulation. Participants treated with low dose aspirin and patients with asymptomatic liver-related coagulopathy not on treatment, may be enrolled into the study.
- 13. Recipients who have any serious condition, which might significantly affect the outcome of the study or their ability to participate in the study.
- 14. History of hypersensitivity to any constituent of the product (any of the study drugs) or its excipients or to drugs of similar chemical classes.
- 15. Recipients with HIV positive donor.
- 16. Recipients with donors HBsAg positive.
- 17. Recipients who are HCV antibody-positive without documented sustained viral response (SVR) at 12 weeks after finishing anti HCV treatment (e.g., direct-acting antivirals).

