Chemistry	Albumin, alkaline phosphatase, total bilirubin, bicarbonate, calcium, total cholesterol, chloride, creatinine(*), CPK, gamma-GT, (fasting plasma) glucose, HbA1c, HDL, LDL, ratio of total cholesterol to HDL, ratio to LDL to HDL, inorganic phosphorus, lipase, amylase, magnesium, potassium, total Immunoglobulin G (IgG), total protein, AST, ALT, sodium, triglycerides, blood urea nitrogen (BUN) and uric acid. If the total bilirubin concentration is increased above 1.5 times the upper limit of normal, direct and indirect reacting bilirubin should be differentiated.
	(*) Serum creatinine (local) prior to the time of randomization or anytime thereafter if not available at the central laboratory.
Urinalysis	Protein, creatinine, albumin, glucose; proteinuria and albuminuria will be estimated from spot protein/creatinine and albumin/creatinine ratios.
	If the (macroscopic panel) dipstick result is positive for protein, nitrite, leucocytes and/or blood the sample will be sent for microscopic analysis of WBC, RBC and casts.
Coagulation	International normalized ratio (INR), prothrombin time (PT), partial thromboplastin (PTT) and activated partial thromboplastin time (aPTT).
Viral serology	Qualitative viral serology for donors/recipients evaluated for screening and/or baseline will be performed by local laboratories.
	It includes:
	 Hepatitis serology: hepatitis B surface antigen (HBsAg), antibodies to hepatitis B virus (anti-HBc and anti-HBs) and antibody to hepatitis C virus (anti-HCV).
	Human immunodeficiency virus (HIV).
	 Qualitative viral serology tests for cytomegalovirus (CMV) and Epstein Barr virus (EBV) (IgG and IgM).
	Quantitative viral serology test for EBV and CMV will be assessed locally if active infection is suspected. It is highly recommended to quantify the EBV and CMV viremia and record the results on the corresponding CRF pages (number of copies/mL and method used).
	Qualitative and/or quantitative HCV-RNA and HBV-DNA (using PCR) will be performed locally for those participants who are tested anti-HCV positive and HBsAg positive, respectively.
Additional tests:	A-fetoprotein, MMF trough levels, PK, PD (soluble CD40) and immunogenicity (anti-CFZ533 antibodies) blood samplings.
Pregnancy Test	Serum (local laboratory)/Urine.

 Table 8-5
 Laboratory Assessments

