10.1 Definition of adverse events and reporting requirements

10.1.1 Adverse events

An adverse event (AE) is any untoward medical occurrence (e.g., any unfavorable and unintended sign, including abnormal laboratory findings, symptom or disease) in a clinical investigation participant after providing written informed consent for participation in the study. Considering that the screening period may be up to 2 months long, recording of AEs will start from Baseline/LTx date onwards. Therefore, an AE may or may not be temporally or causally associated with the use of a medicinal (investigational) product. Novartis qualified medical personnel will be readily available to advise on trial related medical questions or problems.

In addition, all reports of intentional misuse and abuse of the product are also considered an adverse event irrespective if a clinical event has occurred.

The investigator has the responsibility for managing the safety of individual participants and identifying adverse events.

The occurrence of adverse events must be sought by non-directive questioning of the participant at each visit during the study. Adverse events also may be detected when they are volunteered by the participant during or between visits or through physical examination findings, laboratory test findings, or other assessments.

Novartis qualified medical personnel will be readily available to advise on trial related medical questions or problems.

Abnormal laboratory values or test results constitute adverse events only if they fulfill at least one of the following criteria:

- they induce clinical signs or symptoms,
- they are considered clinically significant,
- they require therapy.

Clinically significant abnormal laboratory values or test results must be identified through a review of values outside of normal ranges/clinically notable ranges, significant changes from baseline or the previous visit, or values, which are considered non-typical in participant with underlying disease. Investigators have the responsibility for managing the safety of individual participant and identifying adverse events. Alert ranges for laboratory and other test abnormalities are included in Appendix 1.

Adverse events must be recorded under the signs, symptoms or diagnosis associated with them, accompanied by the following information (as far as possible) (if the event is serious refer to Section 10.1.2):

- the severity grade. If severity grade is selected, add the following:

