Data collected on AE CRFs will be coded with the MedDRA dictionary that gives preferred term (PT) and system organ class (SOC) information. AEs and infections data will be analyzed as a whole under the heading of AEs for each treatment arm. If a participant has multiple occurrences of an AE, the participant will only be counted once in the corresponding AE category. If participant has multiple AEs within a SOC, the participant will be counted only once for that SOC. If a participant has multiple severity ratings for an AE, the participant will be counted under the maximum rating.

Incidence rates of safety topics of interests from eCRS will be summarized by risk categories. Safety topics of interests are defined in Table 2-2.

Safety topics of interests	Search strategy	
Infections	MedDRA search strategy SOC "Infections and infestations" [10021881] and HLGT "Microbiology and serology investigations" [10027529].	
Malignancies including Lymphoproliferative disorder	SMQ Malignant or unspecified tumours (Narrow) (20000091), SMQ Malignancy related therapeutic and diagnostic procedures (20000093) and SMQ Tumour markers (20000094)	
Thrombosis	MedDRA search strategy SMQ "Embolic and thrombotic events (SMQ)" [20000081] and HLT "Coagulation and bleeding analyses" [10009728].	

 Table 2-2
 Safety topics of interests

Novartis	
SAP	

Immunogenicity	PT: Drug specific antibody present [10013745]		
	SMQ: Hypersensitivity (Narrow), (20000214)		
Vaccination failure	Therapeutic product ineffective (10060769)		
	Therapeutic response changed (10074941)		
	Therapeutic response decreased (10043414)		
	Therapeutic response delayed (10053181)		
	Therapy non-responder (10051082)		
	Antibody test abnormal (10061425)		
	Antibody test negative (10061426)		
	Immunology test abnormal (10061214)		
	Vaccination failure (10046862)		
	Vaccine breakthrough infection (10067923)		
	Absence of immediate treatment response (10081766)		
	Drug effect less than expected (10083365)		

The AE, SAE, infections, and serious infections summarized as above will also be provided in corresponding listings.

New onset of diabetes mellitus (NODM)

New onset diabetes mellitus is defined as:

- a. All of the following should be true (no diabetes pre-transplantation):
 - 1. Diabetes was not included in the medical history.
 - 2. Glucose (random) < 11.1 mmol/L (200 mg/dL) at the time of transplantation.
 - 3. Diabetes was not recorded as reason for any medication given prior to transplantation.

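### SAP Table 2-2 pools AE-reported laboratory, marker and procedure terms with clinical events under 'Thrombosis' and 'Malignancies', with no clinical-event row

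*SAP*

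**What the plan says.** SAP Section 2.7 states how the topics are reported: "Incidence rates of safety topics of interests from eCRS will be summarized by risk categories". Their source is coded adverse event data, not the central laboratory file: "Data collected on AE CRFs will be coded with the MedDRA dictionary".

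Table 2-2 gives one search per topic.

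- **Thrombosis:** the embolic and thrombotic events SMQ, joined by 'and' to "HLT 'Coagulation and bleeding analyses' [10009728".
- **Malignancies:** the malignant or unspecified tumours SMQ, limited to its narrow scope, and then "SMQ Malignancy related therapeutic and diagnostic procedures (20000093) and SMQ Tumour markers (20000094".
- **Infections:** the infections SOC joined to an HLGT of microbiology and serology investigations, so it has the same structure.

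The table does not say whether 'and' means union, and it does not split clinical events from the other terms.

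Protocol Table 8-5 puts this coagulation panel in the safety laboratory tests: "International normalized ratio (INR), prothrombin time (PT), partial thromboplastin (PTT) and activated partial thromboplastin time (aPTT". Protocol Section 10.1.1 limits when a test result becomes an adverse event: "Abnormal laboratory values or test results constitute adverse events only if they fulfill at least one of the following criteria". The criteria are that it induces signs or symptoms, is clinically significant, or requires therapy.

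**The concern.** The group names alone show the mixture. A set of coagulation and bleeding analyses is counted as thrombosis, although an abnormality in such a test may point to bleeding rather than clotting. Likewise, the malignancy search first restricts its tumour SMQ to narrow scope and then widens the topic again with markers and procedures.

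This matters because Protocol Section 4.6 lists thrombophilia and lymphoproliferative disorders among the potential risks of CFZ533, and Protocol Section 8.4.4 describes hepatic artery thrombosis as frequent in this population. SAP Section 2.13 includes the topics in the interim safety analyses, whose stated purpose is overall benefit-risk assessment.

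There is also no cleaner aggregate to fall back on for thrombosis. Protocol Section 12.5.2.2 planned adverse event summaries by SMQ and preferred term, but the list in SAP Section 2.7 does not carry the by-SMQ summary forward. The mixed row in Table 2-2 is then the only aggregate thrombosis incidence that the SAP specifies.

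**Working it through.** The documents state no rate, power or sample size for these topics, so there is no figure of the plan's own to reproduce. All event rates below are assumptions, chosen to show direction and scale.

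**Formula.** Let p be the true proportion with a clinical event in an arm, and q the proportion of participants without one who have a laboratory-only (or marker-only) adverse event. Each participant counts once per category (SAP Section 2.7), so the observed proportion is

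p' = p + (1 - p)q.

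With the same q in both arms, the difference is p'(CFZ533) - p'(control) = (1 - q) × [p(CFZ533) - p(control)].

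**Equal reporting, assumed true rates 5% control v 10% CFZ533:**

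| q | Control | CFZ533 | Difference (points) | Ratio |
|---|---|---|---|---|
| 0 | 5.0% | 10.0% | 5.0 | 2.00 |
| 5% | 0.05 + 0.95×0.05 = 9.75% | 0.10 + 0.90×0.05 = 14.5% | 4.75 | 1.49 |
| 10% | 0.05 + 0.95×0.10 = 14.5% | 0.10 + 0.90×0.10 = 19.0% | 4.5 | 1.31 |
| 20% | 0.05 + 0.95×0.20 = 24.0% | 0.10 + 0.90×0.20 = 28.0% | 4.0 | 1.17 |

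A larger assumed effect behaves the same way. For 5% v 20%, q = 10% gives 14.5% v 28.0%: the difference falls from 15.0 to 13.5 points and the ratio from 4.0 to 1.93. The ratio is diluted strongly and the difference only modestly.

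**Unequal reporting.** The trial is open-label to investigators and the sponsor team (Protocol Section 6.4), so equal q cannot be taken for granted.

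- True 5% v 10%, q = 5% control and 20% CFZ533: 9.75% v 0.10 + 0.90×0.20 = 28.0%. The difference is 18.25 points and the ratio 2.87, both inflated.
- True 5% v 10%, q = 20% control and 5% CFZ533: 24.0% v 14.5%. The difference is -9.5 points, so the sign is reversed.
- True 5% v 20%, q = 20% control and 5% CFZ533: 24.0% v 0.20 + 0.80×0.05 = 24.0%. The difference is erased.

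**Scale per participant.** At the planned arm sizes of 48 and 32 (Protocol Section 12.7), one laboratory-only participant moves the topic incidence by 1/48 = 2.1 points in a CFZ533 arm and 1/32 = 3.1 points in the control arm.

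**The case against.** A reader might infer that any raised INR or alpha-fetoprotein scores as an event, and that the effect is to dilute a true arm difference. The documents support neither.

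- **A value does not score by itself.** It must be reported as an adverse event under Protocol Section 10.1.1 and be treatment-emergent under SAP Section 2.7. This keeps q below the frequency of abnormal results. Exclusion criterion 12 does say that "patients with asymptomatic liver-related coagulopathy not on treatment, may be enrolled into the study", but a stable pre-existing condition is not treatment-emergent unless it worsens.
- **Alpha-fetoprotein is not a routine post-randomization test for everyone.** Footnote 4 to Protocol Table 8-1 sets it at baseline, at randomization for HCC participants, and then as needed. A marker event may accompany a genuine recurrence.
- **Term membership is inferred.** Neither document lists the preferred terms in these groups.
- **The direction is not fixed.** Dilution requires similar reporting in the arms, as shown above.

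There are also other routes to clean counts. Adverse events are tabulated by SOC and/or preferred term and are listed. Protocol Sections 8.4.4 and 10.1.2 make every malignancy serious, and the SAP summarizes malignancies under SAEs. For malignancy this largely answers the point. For thrombosis it does so only in part: participants can have several terms, so preferred-term counts cannot be added into an incidence without working through the participant listings.

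Finally, a broad search for descriptive screening is a legitimate trade of specificity for sensitivity. That stands, and it is a reason to keep the full search rather than remove terms from it. It is not a reason to leave the components unseparated.

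**Conclusion.** The point holds as a reporting weakness. The Thrombosis and Malignancies topics mix clinical events with AE-reported investigation, marker and procedure terms, so a single incidence cannot be interpreted for the named risks. This rests on reading 'and' as union and on the group names describing their contents.

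The size is unknown, because the documents give neither true event rates nor the rate of laboratory-only adverse events. Under equal reporting, the risk difference is reduced only by the factor (1-q) and the ratio by more. Under unequal reporting, the comparison can be inflated, erased or reversed.

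The consequence is limited. The topics carry no test or success criterion, and the stopping rules use BPAR and serious infections instead. A reader might infer that the mixed row hid a thrombosis signal or shaped the decision to terminate. The documents show only that the topics were among the planned interim safety analyses, and say nothing of what they contributed. This is a cheap improvement to presentation and does not challenge any conclusion of the trial.

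**What to change.** In SAP Table 2-2 and the matching outputs:

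1. Keep the full search as the topic total, so no hit is lost, and state that 'and' means union.
2. Under each topic add a clinical-event row: the embolic and thrombotic events SMQ for Thrombosis, and the malignant or unspecified tumours SMQ (narrow) for Malignancies.
3. Add a second row for participants whose only qualifying terms are investigation, marker or procedure terms.
4. Check the terms retrieved by each group against the MedDRA version used.
5. Treat Infections the same way, separating the microbiology and serology investigations HLGT from the infections SOC.

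The cost is a wording change and a few extra table rows from data already collected and coded. The total keeps its present sensitivity, so the only downside is a longer table.

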Risks: the potential safety concerns in humans and the investigator guidance are based on data from the available clinical trials with CFZ533, preclinical and toxicological data, as well as experience with other compounds of the same class (refer to the current investigator brochure).

Beyond the potential risks described in the Investigator Brochure (IB), there may be risks that may be serious and unforeseen in relation to the use of CFZ533.

The risk to subjects in this trial will be minimized by adherence to the eligibility criteria; close clinical monitoring and adherence to the protocol defined stopping rules (refer to Section 12.6).

Novartis	Confidential	Page 50 of 136
Amended Clinical Trial Protocol (Version No.	04 clean)	Protocol No. CCFZ533A2202

The list of potential risks related to CFZ533 administration, in the current Investigator Brochure include those generally associated with administration of a monoclonal antibody in humans. These include the possibility of a hypersensitivity reaction (characterized by acute or delayed allergic reaction, anaphylaxis, urticaria, rash, dyspnea, hypotension, fever, chills), immunogenicity, infections, therapeutic failure of vaccination during CFZ533 treatment, loss of efficacy or allergic/immune-mediated inflammatory reactions due to development of anti-CFZ533 antibodies, thrombophilia and lymphoproliferative disorders (refer to the actual IB for more details). A serious infusion reaction that results in anaphylaxis could happen in monoclonal antibody therapy.

As with any therapeutic protein, immunogenicity is always a risk, although it is important to note that CFZ533 is a fully human monoclonal antibody (lower risk compared to humanized or chimeric antibodies) with immunosuppressive properties and that will be co-administered with MMF, further limiting the risk for the generation anti-CFZ533 antibodies.

During a Public Health emergency as declared by Local or Regional authorities, i.e., pandemic, epidemic or natural disaster, mitigation procedures to ensure participant safety and trial integrity are listed in relevant sections. Notification of the Public health emergency should be discussed with Novartis prior to implementation of mitigation procedures, and permitted/approved by Local or Regional Health Authorities and Ethics Committees as appropriate.

4.7 **Previous clinical experience with CFZ533**

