 - mild: usually transient in nature and generally not interfering with normal activities
 - moderate: sufficiently discomforting to interfere with normal activities
 - severe: prevents normal activities
- its relationship to the study treatment and other investigational treatment. If the event is due to lack of efficacy or progression of underlying illness (i.e., progression of the study indication) the assessment of causality will usually be 'Not suspected.' The rationale for this guidance is that the symptoms of a lack of efficacy or progression of underlying illness are not caused by the trial drug, they happen in spite of its administration and/or both lack of efficacy and progression of underlying disease can only be evaluated meaningfully by an analysis of cohorts, not on a single participant.
- its duration (start and end dates) or if the event is ongoing an outcome of not recovered/not resolved must be reported
- whether it constitutes a serious adverse event (SAE See Section 10.1.2 for definition of SAE) and which seriousness criteria have been met
- action taken regarding with study treatment

All adverse events must be treated appropriately. Treatment may include one or more of the following:

- no action taken (e.g., further observation only)
- study treatment interrupted/withdrawn
- concomitant medication or non-drug therapy given
- non-drug therapy given
- participant hospitalized/participant's hospitalization prolonged (see Section 10.1.2 for definition of SAE)
- its outcome not recovered/not resolved; recovered/resolved; recovered/resolved with sequelae; fatal; or unknown

Conditions that were already present at the time of informed consent should be recorded in medical history of the participant.

Adverse events (including lab abnormalities that constitute AEs) should be described using a diagnosis whenever possible, rather than individual underlying signs and symptoms.

Adverse event monitoring should be continued until EOS visit. After EOS, only the SAEs will be reported to the Novartis safety database for a period of 14 weeks from the last CFZ533 injection.

Once an adverse event is detected, it must be followed until its resolution or until it is judged to be permanent (e.g. continuing at the end of the study), and assessment must be made at each visit (or more frequently, if necessary) of any changes in severity, the suspected relationship to the study drug, the interventions required to treat it, and the outcome.

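### SAP Table 2-2 counts ten terms with no stated vaccine link in the Vaccination failure topic, so the row can include events unrelated to any vaccine

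*SAP*

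**What the plan says.** SAP Section 2.7 states that "Incidence rates of safety topics of interests from eCRS will be summarized by risk categories", and that "Safety topics of interests are defined in Table 2-2". No other definition of the topics is given.

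The Vaccination failure row of Table 2-2 is a list of individual terms. It includes "Therapeutic product ineffective (10060769", "Therapeutic response changed (10074941", "Therapeutic response decreased (10043414" and "Drug effect less than expected (10083365" alongside the two terms that name vaccination or a vaccine.

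The risk that the row serves is in Protocol Section 4.6, which lists "therapeutic failure of vaccination during CFZ533 treatment" among the potential risks of CFZ533. SAP Section 2.13 also includes the safety topics in the interim safety analyses. The stated purpose of that interim is the overall benefit-risk assessment.

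**The concern.** The row label makes a specific claim, that a vaccination failed. Most of the terms behind it do not. An adverse event coded as non-response to an antiviral, an antifungal or an immunosuppressant meets the definition with no vaccine involved. So does an unspecific antibody result that is reported as an adverse event.

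A reader of the study report will take the label at face value as the incidence of a named potential risk. If lack-of-effect reporting differs between arms for reasons unrelated to vaccines, the row moves with it. The study is open-label (Protocol Section 6.4), so such a difference in reporting is possible even where the true rates are equal.

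**Working it through.** There is no sample size, power or event figure to reproduce. The check is to count the terms in the row, sort them by what they name, and look in both documents for any condition that limits them.

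**Step 1: count (SAP Table 2-2, Vaccination failure row).**

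| Group | Terms | Count | Share |
|---|---|---|---|
| Names a vaccine or vaccination | Vaccination failure; Vaccine breakthrough infection | 2 | 2/12 = 17% |
| Lack of effect, any therapy | product ineffective; response changed, decreased or delayed (three terms); non-responder; no immediate treatment response; effect less than expected | 7 | 7/12 = 58% |
| Test result, no antigen named | antibody test abnormal; antibody test negative; immunology test abnormal | 3 | 3/12 = 25% |

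Non-specific terms: 7 + 3 = 10, and 10/12 = 83%.

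**Step 2: look for a limiting condition.** Neither document restricts these ten terms to vaccines, links them to a recorded vaccination, or asks for medical review of the hits. The SAP does write a review step where it wants one: Section 2.3.1 has the corticosteroid list medically reviewed before analysis. No equivalent is stated for this row.

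**Step 3: can non-vaccine events reach these terms?**
- Protocol Section 10.1.1 gives causality guidance that begins "If the event is due to lack of efficacy or progression of underlying illness", so adverse events of that kind are foreseen.
- Protocol Section 6.2.1 allows treatment or prophylaxis for CMV, Pneumocystis, hepatitis B and Candida. Failure of any of these could be coded to a lack-of-effect term.
- Protocol Table 8-5 includes hepatitis, CMV and EBV serology. Under Section 10.1.1, an abnormal result is an adverse event only if it causes symptoms, is clinically significant or needs therapy. That route is open but narrow.

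**Step 4: size.** Let p be the proportion of an arm with a treatment failure and s the share of those also reported under one of the seven lack-of-effect terms. The false incidence is p × s. The documents give no value for s.
- At s = 0 the effect is nil.
- With the planned control rate of 10% and the highest CFZ533 rate in SAP Table 3-2, 15%, an assumed s = 0.10 gives 0.10 × 0.10 = 1.0% and 0.15 × 0.10 = 1.5%.
- In participants this is 0.010 × 32 = 0.32 and 0.015 × 48 = 0.72, less than one per arm.

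**Step 5: where the row is used.** It appears in the safety-topic summary of the study report (SAP Section 2.7) and in the interim safety analyses (Section 2.13). The primary and key secondary analyses (Sections 2.4 and 2.5) do not use it. The stopping rules (Section 3.1) rest on centrally read rejection and serious infections.

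**The case against.** The strongest reply is that Table 2-2 is a retrieval strategy and is broad by design. Its other rows also take in wide groups, such as coagulation analyses under thrombosis and tumour markers under malignancies. A sensitive search for a rare risk is reasonable. Adverse events are also summarised by system organ class and/or preferred term, and they are listed (SAP Section 2.7), so a careful reader could find which terms drove the row. The case retrieval strategy itself is not in the documents, so any handling of hits there cannot be judged.

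Much of this stands, and it is why the full search should be kept. It does not justify a label that claims more than ten of the twelve terms can show. Going back to the listings is no substitute for a row that means what it says.

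A reader might go further and infer that steroid-resistant rejections will be reported as failed vaccinations. The documents do not support that:
- Protocol Section 10.1.1 asks for adverse events to be described by diagnosis where possible, and the row contains no rejection term.
- Steroid resistance is a field on the Liver Allograft Rejection eCRF (SAP Section 5.4.1), which Table 2-2 does not use.
- The lack-of-efficacy text in Protocol Section 10.1.1 is conditional guidance on causality, not an instruction to report such events.

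A reader might also build a larger contrast, such as 25% failure against 10% with one failure in five double-reported. That gives 0.25 × 0.20 = 5% against 0.10 × 0.20 = 2%, or 2.4 of 48 participants against 0.64 of 32. The one-in-five share has no source, and 25% lies above the 7% to 15% range planned for CFZ533 in SAP Table 3-2.

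**Conclusion.** The definition is broader than its label. Ten of 12 terms (83%) carry no stated link to a vaccine, and an event coded to any of them counts as a vaccination failure. That follows from the text and needs no assumption.

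The practical size is unknown and probably low. A false hit needs a separate adverse event worded as drug non-response, or a test result that itself qualifies as an adverse event. The percentages in the working are illustrations that rest on an assumed reporting share.

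The consequence is limited to one descriptive safety-topic row, in the study report and at the interim. The SAP introduction says that the study ended after the interim analysis because the risk-benefit was no longer favourable. A reader might infer that this row contributed, but nothing in the documents says so. The point is minor and worth correcting because the correction is cheap.

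**What to change.** Keep all 12 terms, so that sensitivity is not lost, and report the topic in two rows:

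1. **Vaccination failure**: the two vaccine-specific terms.
2. **Possible vaccination failure / non-specific lack-of-effect or antibody-test terms**: the other ten, shown by preferred term.

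Move a hit from the second row to the first only when the verbatim adverse event term names a vaccine. Apply the same split wherever the topic is reported.

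This uses data already coded and drops no event. The cost is one extra table row and a small check of verbatim terms. A genuine vaccine failure whose verbatim term names no vaccine stays in the second row, where it is still visible.

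Requiring a vaccine on the concomitant medication page before the event would work less well. Any earlier vaccine would still admit an unrelated drug non-response. Vaccines given before enrolment may not be recorded either: Protocol Section 5.1 requires vaccination to be up to date at screening, while Section 6.2.1 asks for medications given after enrolment.
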